6.6 Metabolomics testing

Post-test residual serum samples were collected from subjects on day 1 after admission, day 6 postoperatively, 1 month postoperatively, 3 months postoperatively, and 6 months postoperatively for metabolomics testing.

7. Criteria for evaluating the efficacy of treatment

7.1 Nutritional indicators

Primary Efficacy Indicator:

Serum albumin (ALB), recording ALB data from patient biochemical tests.

Secondary efficacy indicators:

Prealbumin (PA), alanine aminotransferase (ALT), glutamate aminotransferase (AST), serum gamma-glutamyl transpeptidase (GGT), cholinesterase (CHE), total bilirubin (TBIL), and C-reactive protein (CRP) were recorded, and the corresponding data in the patient's biochemical tests were recorded;

7.2 Clinical outcomes

1) Post-operative complications

a) Postoperative infections: surgical site infections (SSI), remote infections (RI) and bacteremia.

SSI: Shallow/deep incision SSI and organ/space SSI were defined as redness, swelling, heat, pain, and purulent discharge observed in any incision or space operated on intraoperatively, or the need for a new drain within 30 days postoperatively.

Distant infections: including cholangitis, enteritis, pneumonia, catheter-related infections, and urinary tract infections, defined as fever greater than 38.5°C, leukocytosis, and bacteria detected in

sputum, catheter tips, and urine and feces.

Bacteremia: Bacteremia is diagnosed when a strain is cultured from a single blood culture. And when the strain is identified as coagulase-negative staphylococci, it is considered contaminating; coagulase-negative staphylococci may be considered the causative agent when isolated from two or more blood cultures.

b) Bile leakage

Fluid with a bilirubin concentration of at least three times the serum bilirubin concentration drained through an abdominal drain on or after postoperative day 3. Regardless of the initial bilirubin concentration of the drain placed through surgery, the need for radiologic (i.e., interventional drainage) or surgical intervention (i.e., relative to cesarean section) for biliary collection or biliary peritonitis is also part of the diagnosis of bile leakage.

c) Liver failure after hepatectomy

Elevated serum bilirubin concentration and elevated INR on or after postoperative day 5 compared to the previous day; or coagulation factors such as fresh frozen plasma (FFP) are required to maintain normal INR values on or after postoperative day 5 in combination with hyperbilirubinemia.

- 2) Total hospitalization cost: the total cost of the patient from admission to discharge;
- 3) Recurrence-free survival: the time from the start of the patient's hepatectomy to the first detection of tumor recurrence;
- 4) Quality of Survival: Quality of Survival was evaluated by the EORTC QLQ - HCC18 scale (Appendix 1);
- 5) Safety, diarrhea, vomiting: complaints of gastrointestinal distress that occur after the patient has initiated nutritional support therapy, with diarrhea defined as unformed stools more than three times per day.

8. Adverse Events Watch

Adverse events (AEs), all adverse medical events that occur after a subject receives a late-night snack, which can be manifested as symptoms signs, illnesses, or abnormal laboratory tests, but are not necessarily causally related to the late-night snacks.

Serious Adverse Event (SAE), an adverse medical event such as death, life-threatening, permanent or severe disability or loss of function, subject requiring hospitalization or prolonged hospitalization, and

congenital anomalies or birth defects that occur after a subject receives late-evening snacks.

The investigator will closely observe or follow up the various reactions of the patients after performing the LES in order to detect adverse events or serious adverse events in a timely manner, and all adverse events such as bloating, diarrhea, etc., reported by the subjects or observed by the investigator during the period from enrollment to the end of the study or early withdrawal from the study must be documented in the medical record or CRF, including laboratory and ancillary investigations, and should include, at a minimum, the name of the AE, its occurrence time (to the nearest minute), end time (to the nearest minute), degree and frequency of episodes, whether or not treatment was corrected, the course of treatment and regression if treatment was documented, and the causal relationship to the study. All medical documentation related to the adverse event must be recorded in the original documentation, including copies of requests for laboratory tests and reports of test results. The name of the investigator must be signed and dated (to the nearest minute) on the original documents and written reports.

Changes in the subject's vital signs, physical examination, clinical manifestations, and laboratory tests should be evaluated during the study. At the time of signing the informed consent form, the name and telephone number of an investigator whom the subject can contact in case of an emergency, or report of any medical symptom, or occurrence of an AE related to the subject must be provided. The investigator should follow up all adverse events and serious adverse events, decide the duration of follow-up according to the condition, and give necessary treatment and therapeutic measures during follow-up until proper resolution or stabilization of the condition, and in case of abnormal laboratory tests should be followed up until the return visit is normal to ensure that the damage to the subject is minimized. Detailed records of the follow-up visits and treatment results should be kept.

Toxic reactions or AEs that existed prior to the subject's participation in the clinical study were recorded as AEs only if the grading was found to have increased by one or more grades from the baseline assessment during the study.

CTCAE classification	equivalent to	definition
Level 1	mildly	Mild discomfort that does not affect daily life or functioning
Level 2	moderately	Unwell, interfering with daily life and function,

		no indication for treatment
Level 3	severe	Symptomatic, affecting daily life and function, with indication for treatment
Level 4	Life threatening/disability/loss of function	Life-threatening conditions, indications for emergency treatment, physically or mentally handicapped conditions
Level 5	death	Adverse events leading to death.

AE and study correlation analysis table

	Definitely	Likely	Possible	Suspicious	unlikely
Reasonable timing with medications/interventions	+	+	+	+	-
Known types of drugs/reactions	+	+	+	+	-
Reduction or disappearance of symptoms with cessation of intervention	+	+	±	±	-
Response recurs after another intervention	+	?	?	?	-
Cannot be explained by disease, comorbidities	+	+	-	±	-

9. Data security monitoring

A data safety monitoring program will be established for clinical studies according to the level of risk. All adverse events will be recorded in detail, appropriately handled and followed up until properly resolved or stabilized, and serious adverse events and unintended events, etc., will be reported to the Ethics Committee, the competent authority, the sponsor, and the drug regulatory authority in a timely manner according to the regulations; the principal investigator will conduct a cumulative review of all adverse events on a regular basis, and convene a meeting of the investigators to assess the risks and benefits of the study, if necessary; the injuries or discomfort is no more likely and no greater in magnitude than that encountered in daily life or than that of a routine examination, and that data and safety monitoring can be accomplished by the principal investigator.

10. Statistical processing

应用 SPSS26.0 统计软件对临床数据进行描述性统计，符合正态分布的计量资料以均数±标

准差($\bar{x} \pm s$)表示, 组间采用 t 检验, 不符合正态分布的计量资料以中位数(四分位间距) [M(IQR)] 表示, 组间采用 Mann-Whitney U 检验。计数资料用百分比[n(%)]表示, 组间比较采用卡方检验, $P<0.05$ 为有显著性统计学意义。采用 STATA12.0 中的 Kaplan-Meier 法计算各组复发率及无复发生存期, log-rank 检验进行组间比较。SPSS26.0 statistical software was applied to carry out descriptive statistics of the clinical data, and the measurements that conformed to normal distribution were expressed as mean \pm standard deviation ($\bar{x} \pm s$), and t-test was used between the groups, and the measurements that did not conform to normal distribution were expressed as median (inter-quartile spacing) [M(IQR)], and Mann-Whitney U-test was used between the groups. Count data were expressed as percentages [n(%)], and the chi-square test was used for between-group comparisons, with $P<0.05$ considered statistically significant. The Kaplan-Meier method in STATA 12.0 was used to calculate the recurrence rate and recurrence-free survival in each group, and the log-rank test was used for between-group comparisons.

11. Ethical principles of clinical research

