	
his/her supplementation must be completed before 1h before bedtime.
 
2. Biological sample collection:
 
The remaining post-test serum samples need to be collected for metabolomics analysis from patients on day 1 of admission, postoperative day 6, postoperative 1 month, postoperative 3 months, and postoperative 6 months.
 
3. Clinical data collection:
 
1) General information: gender, age, height, weight, BMI, ICG 15min retention time, name of surgery, duration of surgery, blood loss, blood transfusion, tumor stage, NRS2002, GLIM malnutrition assessment (diagnostic) criteria diagnosis.
 
2) Nutritional indicators: Nutritional indicators such as serum albumin (ALB), prealbumin (PA), transferrin (TRF), and total serum protein (TP) were collected from patients on the 1st day of admission, the 6th postoperative day, 1 month postoperatively, 3 months postoperatively, and 6 months postoperatively.
 
(3) Liver function indexes: Liver function indexes such as alanine aminotransferase(ALT), alanine transaminase(AST), γ-glutamyltransferase (GGT), cholinesterase (CHE), and total bilirubin (TBIL) were collected on the 1st day of admission, the 6th postoperative day, 1 month postoperatively, 3 months postoperatively, and 6 months postoperatively.
 
(4) Clinical outcome: collect the patients' postoperative clinical outcome indicators, such as: postoperative complication rate, recurrence-free survival, and quality of survival.
 
(5) Medical costs: collect the total cost of the patients' hospitalization, the cost of anti-infective drugs, and the cost of albumin during hospitalization.

Evaluation of the	
Indicators of effectiveness evaluation
 
Main efficacy indicators: serum albumin (ALB)
 
Secondary efficacy indicators: serum prealbumin (PA), alanine

efficacy of treatment	aminotransferase (ALT), azelaic transaminase (AST), cholinesterase (CHE), total bilirubin (TBIL), total hospitalization costs, relapse-free survival, and quality of life
	
Safety evaluation indicators
 
Incidence of gastrointestinal symptoms such as abdominal distension, diarrhea, nausea and vomiting, incidence of postoperative complications, and length of postoperative hospitalization

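### A new drain alone counts as a surgical-site infection, and the distant-infection rule fits cholangitis and enteritis poorly, so the infection component of the complication outcome is unreliable

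*Combined protocol and SAP*

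**What the plan says.** Section 7.2 (Clinical outcomes), item 1, has three headings: postoperative infections (1a), bile leakage (1b) and liver failure (1c).

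- **SSI (1a).** The first limb, for incisional and organ/space SSI alike, rests on local signs: "defined as redness, swelling, heat, pain, and purulent discharge observed in any incision or space operated on intraoperatively". The second limb is an alternative and has no further condition attached: "or the need for a new drain within 30 days postoperatively".
- **Distant infection (1a).** One definition serves five diagnoses, "including cholangitis, enteritis, pneumonia, catheter-related infections, and urinary tract infections". The shared criterion is "defined as fever greater than 38.5°C, leukocytosis, and bacteria detected in" one of four specimen types, which the plan lists as "sputum, catheter tips, and urine and feces".
- **Bacteremia (1a).** A separate component: "Bacteremia is diagnosed when a strain is cultured from a single blood culture", with an exception for coagulase-negative staphylococci.
- **Bile leakage (1b).** Besides the drain-fluid bilirubin criterion, a collection of bile or a biliary peritonitis makes the diagnosis when there is "the need for radiologic (i.e., interventional drainage) or surgical intervention".

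The synopsis lists "incidence of postoperative complications, and length of postoperative hospitalization" among the safety indicators. Section 2.1 names the complication rate in the primary purpose. Section 5.1, item 5, compares it between groups to learn whether outcomes improve under LES. Section 3.1 describes the grouping as non-randomized, open and by patient preference.

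**The concern.** An infection definition should separate infected from uninfected patients, and these definitions fail to do so in three places.

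1. The drain limb is joined by *or* to the local signs and stands alone. It asks for no pus, culture or other evidence of infection.
2. Drainage of a biliary collection already has a home in 1b. The same event therefore meets two components, and the plan does not say whether the rate counts patients or events.
3. The specimen list for distant infection does not match two of the diagnoses it serves. Cholangitis has no bile specimen, and enteritis is confirmed by bacteria in stool with no pathogen, toxin or threshold named.

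At stake is what the trial can say about infection. If LES is reported to change the infection rate, a reader cannot tell infection from fluid collections that needed drainage. Whether to place a drain or send a specimen is a clinician's decision in an open study, so the classification could also differ by group.

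**Working it through.** **The plan's own figure.** The only sample-size calculation is for albumin (section 3.1): 34.2 ± 3.9 versus 37.5 ± 5.4 g/L, two-sided alpha 0.05, power 90%. The difference is 3.3 and the pooled SD is √((3.9² + 5.4²)/2) = √22.185 = 4.71. Noncentral-t power is 89.5% at 43 per group and 90.1% at 44, so the stated 44 per group (88 in all) is reproduced. Nothing in it depends on the complication definitions.

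**Tracing cases through 7.2 as written.**

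| Case | Components met | Infection component | Event count | Per-patient any-complication rate |
|---|---|---|---|---|
| Sterile biliary collection, new interventional drain on day 10 | SSI and bile leakage | one false infection | 2 instead of 1 | unchanged; already counted under 1b |
| Sterile non-biliary collection at the operated site, new drain | SSI only | one false infection | 1 instead of 0 | rises by one if nothing else is met |
| Cholangitis, bile culture positive, blood negative or not taken | none, unless an unrelated listed specimen is positive | missed | 0 instead of 1 | missed if nothing else is met |
| Cholangitis, blood culture positive (coagulase-negative exception aside) | bacteremia | counted, under another label | 1 | counted |
| Suspected enteritis, fever above 38.5°C, leukocytosis, stool tested | distant infection | counted whatever the stool shows | 1 | counted |

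The last row rests on the general fact that stool normally contains bacteria. The stool limb is then met whenever it is tested, and the definition reduces to fever plus leukocytosis.

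**Illustration of size (all rates assumed; the documents give none).**

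*Count.* If 3% to 8% of 106 patients need a new drain for an uninfected collection, false SSIs number 106 × 0.03 = 3.2 to 106 × 0.08 = 8.5. If the true SSI rate is 5% to 10%, true SSIs number 5.3 to 10.6. The inflation then runs from 3.2/10.6 = 30% to 8.5/5.3 = 160%. Both ends pair opposite extremes of the two ranges.

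*Dilution.* Take true infection rates of 30% and 15% with 53 per group. Let a share f of otherwise infection-free patients in both groups have a sterile drain, so that the observed rate is p + (1 − p)f. Power is from the normal approximation for two proportions, two-sided 0.05.

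| f | Observed rates | Difference (points) | Power |
|---|---|---|---|
| 0 | 30.0% vs 15.0% | 15.0 | 45.5% |
| 2% | 31.4% vs 16.7% | 14.7 | 42.4% |
| 5% | 33.5% vs 19.3% | 14.2 | 38.2% |
| 10% | 37.0% vs 23.5% | 13.5 | 32.6% |

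With equal misclassification in both groups, a true infection effect is diluted. With unequal misclassification the error could go either way, and nothing in the documents fixes which.

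**The case against.** The strongest reply is that this is a component-level issue in a secondary outcome. Count data are given as n (%) and compared by chi-square, which most naturally means patients per group. On that reading the drained sterile bile collection changes nothing overall. Two components overlapping in one patient is ordinary, and section 8 requires adverse events to be documented with laboratory reports, so events could be reclassified later. Most of this stands. It does not rescue the infection rate itself, and the per-patient rule is inferred rather than written.

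A reader might infer several stronger things that the text does not support:

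- *That the complication rate as a whole is misclassified.* The biliary example does not show this for a per-patient rate.
- *That cholangitis goes uncounted.* Cases with a positive blood culture are captured as bacteremia. Only blood-culture-negative or bile-only cases can be lost.
- *That the enteritis definition is empty.* Fever and leukocytosis are still required; only the stool limb is uninformative.
- *That a purulent wound lacking one local sign is not an SSI, or that organ/space SSI is reachable only through a drain.* Both need a strict reading of *and*. The specimen list in the same section also uses *and* and cannot sensibly mean all of them. The English is a loose rendering and will not bear that weight.
- *That a pleural drain is an SSI.* The sentence concerns operated incisions and spaces, so the drain limb is best read as confined to that site.
- *That the definition favours LES.* Section 1 cites less ascites with LES in liver disease, so fewer drains in the test group is conceivable. The documents show neither that this would occur after hepatectomy nor how often.

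**Conclusion.** The point holds for the infection/SSI component. As written, a drained sterile collection is an infection, and a drained sterile biliary collection is both SSI and bile leakage with no rule for counting it. The distant-infection definition offers cholangitis no suitable specimen and gives enteritis a stool limb that does not discriminate. An event count would be inflated. Among sterile drains, only non-biliary ones at the operated site alter a per-patient any-complication rate.

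Confidence is high on the wording and low on its consequences. The 30% to 160% inflation and the fall in power from 45.5% to 32.6% rest wholly on assumed rates, and any between-group bias is a possibility without a known size or direction. Albumin, the primary endpoint, and the sample size are untouched. This should be corrected because the plan tests complications between open groups, but it does not undermine the main analysis.

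**What to change.** In section 7.2, for outcome classification only and without changing care:

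1. Count a new drain at the operated site within 30 days as SSI only when the fluid is purulent or culture-positive.
2. State that a sterile biliary collection counts once, as bile leakage.
3. Give cholangitis and enteritis evidence from their own site: for example bile or blood culture for cholangitis, and a named enteric pathogen or toxin for enteritis, using results already obtained in care.
4. State that the overall rate is the number of patients with at least one complication, with components listed separately.

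The cost is protocol wording and a few CRF fields (reason for drain, appearance of fluid, specimen and result). No extra tests are needed. The documents do not say that drain fluid or bile is routinely cultured, so the CRF should allow *not tested* and the report should give how many drains fall there. The downside is small: the infection rate may be lower and less comparable with series that count any new drain. Reporting the number of patients with any new drain as a separate line would largely restore that comparison.

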3.2 Experimental Steps

The specific steps of the study are as follows:

Pre-procedure preparation:

According to the literature research, establish the form of patients' clinicopathological data that need to be collected, including basic information (age, gender, hospitalization number), pre-surgical laboratory examination (nutritional indexes, liver function, renal function, coagulation function, blood routine, tumor markers such as alpha-fetoprotein, etc.), surgical records (tumor location, size, number, intra-operative bleeding, etc.), post-surgical laboratory examination, tumor recurrence and treatment modality and patient survival, etc., as well as the establishment of a dietary matching table, respectively writing the dietary education content of the experimental group and the control group, in order to personalize the guidance of the patient's postoperative diet and the correct understanding of the importance of dietary therapy. A case questionnaire was set up for the enrolled patients, and the relevant data of the enrolled patients were recorded in the form.

Screening and Trial:

Patients who were admitted to the Department of Hepatobiliary Pancreatic Surgery of Drum Tower Hospital affiliated to Nanjing University School of Medicine, from February 2024 to January 2025 and met the enrollment criteria were selected for inclusion in this study. The grouping was not randomized and blinded, and all patients were enrolled according to their individual wishes and divided into a test group (53 cases) and a control group (53 cases). The purpose of the study, the content of the investigation, the principle of confidentiality were explained to the patients or their families at the time of their admission to the hospital to reduce the concerns of the respondents, and the subjects were included in the study after signing the informed consent form with their consent.

1. Treatment program:

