(2) Postoperative: start drinking small amount of water on the 1st postoperative day, over to liquid diet after ventilation, and may over to autonomous semi-liquid diet + oral whole protein enteral nutrition during the day + LES program on the 2nd postoperative day. As the patient's voluntary intake meets 60% of the body's needs, the daytime oral enteral nutrition support can be gradually stopped and the LES program can be continued.

3) Discharge: daily intake needs to be on time according to the LES regimen.

Control group: no more food 1h before bedtime.

(1) Preoperative: same as the test group.

(2) Postoperative: start drinking small amount of water on the 1st postoperative day, over to liquid diet after ventilation, and can over to autonomous semi-liquid diet + oral whole protein type enteral nutrition during the day on the 2nd postoperative day. As the patient's voluntary intake meets 60% of the body's needs, enteral nutrition support can be gradually stopped.

(3) Discharge: Doctors judge whether the patients need to continue nutritional support according to their dietary recovery, and if they do, their nutritional supplementation should be completed before 1h

before bedtime.

2. biological sample collection:

Serum samples remaining after testing were collected from patients for metabolomics analysis.

3.Clinical information collection:

(1) General information collection: gender, age, height, weight, BMI, ICG15min retention time, name of surgery, duration of surgery, blood loss, blood transfusion, tumor stage, NRS2002, PG-SGA, GLIM malnutrition assessment (diagnosis) criteria diagnosis;

(2) Nutritional indicators collection: collect nutritional indicators such as serum albumin (ALB), prealbumin (PA), transferrin (TRF), and total serum protein (TP) on the 1st day of the subject's admission to the hospital, on the 6th day of the postoperative period, at 1 month after the operation, at 3 months after the operation, and at 6 months after the operation.

(3) Collection of liver function indexes: Liver function indexes such as alanine aminotransferase (ALT), alanine grass aminotransferase (AST), γ -glutamyltransferase (GGT), cholinesterase (CHE), and total bilirubin (TBIL) were collected on the first day of hospitalization, the sixth postoperative day, the first postoperative month, the third postoperative month and the sixth postoperative month of the subjects.

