6.3 Liver function indicators

The patients' alanine aminotransferase (ALT), alanine transaminase (AST), γ -glutamyl transferase (GGT), cholinesterase (CHE), and total bilirubin (TBIL) were collected on the 1st day of the patients'

admission, on the 6th day of the postoperative period, at 1 month postoperatively, at 3 months postoperatively, and at 6 months postoperatively.

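### The first limb of the liver-failure definition counts any joint day-on-day rise in bilirubin and INR, has no reference level, and cannot be judged from the scheduled tests

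*Combined protocol and SAP*

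**What the plan says.** **Definition.** Section 7.2, item 1, lists three kinds of postoperative complication: infection, bile leakage and liver failure. Liver failure (1c) is met by either of two limbs:

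- Limb 1: "Elevated serum bilirubin concentration and elevated INR on or after postoperative day 5 compared to the previous day".
- Limb 2: clotting factors, with fresh frozen plasma as the example, "are required to maintain normal INR values on or after postoperative day 5 in combination with hyperbilirubinemia".

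Neither limb states a cut-off, an upper limit of normal, a minimum rise or a persistence requirement. Other definitions in the same section do carry numbers: a threefold ratio for bile leakage, 38.5°C for fever, and three stools a day for diarrhea.

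**Testing.** In Section 3.2, clinical information item (3), the transaminases, GGT, cholinesterase "and total bilirubin (TBIL) were collected on the first day of hospitalization, the sixth postoperative day, the first postoperative month", and again at 3 and 6 months. Section 6.3 repeats the schedule: "on the 6th day of the postoperative period, at 1 month postoperatively". Neither panel contains INR or prothrombin time. Coagulation is named for the data form only before surgery: "pre-surgical laboratory examination (nutritional indexes, liver function, renal function, coagulation function, blood routine". The same sentence of Section 3.2 also lists "post-surgical laboratory examination, tumor recurrence and treatment modality", without saying which tests or which days. Section 6.5 has complications and symptoms recorded daily in hospital. Section 8 asks for laboratory changes to be evaluated during the study, again without naming tests.

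**Use.** The synopsis lists postoperative complications under safety. Section 2.1 puts the complication rate in the primary purpose, and Section 5.1, item 5, compares it between groups. Section 3.1 makes the grouping open and a matter of each patient's preference.

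**The concern.** An outcome rule should classify the same patient in the same way whoever looks and however often blood is drawn. Limb 1 compares two tests with their own values of the day before and with nothing else. Small joint rises within ordinary variation would count. Values that are very high but steady would not.

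The rule also needs both tests on consecutive days, which the schedule does not provide. Whether a patient can meet limb 1 then depends on how often clinicians order tests. In an open study with self-selected groups, that frequency could differ by arm, and a difference in testing could appear as a difference in liver failure or hide one. Without any such imbalance, false positives shared by both arms would still dilute a true difference.

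**Working it through.** The plan states no event rate, variability or power for liver failure, so there is no figure of its own to reproduce.

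**1. Definition against schedule (no assumptions needed).**

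| Needed for limb 1, from POD5 | Scheduled |
|---|---|
| Bilirubin on day *d* | POD6; later only at 1, 3 and 6 months |
| Bilirubin on day *d* − 1 | none |
| INR on day *d* | none |
| INR on day *d* − 1 | none |

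The scheduled tests yield 0 evaluable day pairs.

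**2. Flat values, exact.** Assume that each test fluctuates around a constant level, independently of the other, with no ties.

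- One day pair: P(both rise) = 1/2 × 1/2 = 25%.
- Two pairs (POD4 to POD6): for three values in random order, the sets of rises {none, first only, second only, both} have counts 1, 2, 2, 1 out of 6. The two tests share no rise with probability (1×6 + 2×3 + 2×3 + 1×1)/36 = 19/36. P(flagged) = 17/36 = 47%.
- Three pairs: the same count over four values gives 365/576 = 63%.

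**3. Other courses, simulated.** 200,000 patients per scenario, tested daily from POD4. None of the following inputs is in the documents: bilirubin 18 µmol/L (CV 10%, reported to 0.1), and INR 1.15 (SD 0.05). In the recovery rows, bilirubin and the INR excess over 1 decline exponentially at 0.1 a day (about 10%) or 0.2 a day (about 20%). The fast row uses CV 5% and SD 0.03. The table gives the share meeting limb 1 at least once by the day shown.

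| Scenario | POD5 | POD6 | POD8 |
|---|---|---|---|
| Flat, INR to 0.01 | 23% | 44% | 71% |
| Flat, INR to 0.1 | 14% | 27% | 48% |
| Falling about 10% a day, INR to 0.01 | 9% | 18% | 35% |
| Falling about 10% a day, INR to 0.1 | 5% | 10% | 18% |
| Falling about 20% a day, INR to 0.01 | 0.1% | 0.1% | 0.2% |

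With independent fluctuations the POD6 range is therefore about 0.1% to 44%. The 44% lies a little below the exact 47% because rounding creates ties. If the two tests fluctuate together (assumed correlation 0.3), the flat case reaches 53% by POD6. The share rises with each added day in the flat and slow-recovery rows. In the fast row it stays very low.

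**4. High plateau.** If bilirubin and INR are constant, each day-on-day difference is 0, so limb 1 fails at any level. Limb 2 catches such a patient only if clotting factors are needed.

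**5. Dilution, as an illustration only.** Assume true rates of 15% and 3%, 53 per arm, and a false-positive share *f* that is equal in both arms. The observed rate is p + (1 − p)*f*. With *f* = 10% this is 0.15 + 0.85 × 0.10 = 23.5% against 0.03 + 0.97 × 0.10 = 12.7%. Power falls from 58% at *f* = 0 to 30%. At *f* = 25% it is 17%.

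**The case against.** Four arguments deserve weight.

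- **Limb 2 exists.** A reader might infer that the whole definition is a day-on-day rise. It is not: limb 2 needs no pair of days and refers to a normal INR and a raised bilirubin. This stands, and it confines the plateau gap to patients who do not need clotting factors. It does not repair limb 1, and hyperbilirubinemia is itself undefined.
- **The word *elevated* may mean above normal and also rising.** The text is a translation, and the wording of limb 2 lends this some support. Patients with normal values would then not be flagged. But no limit of normal is given, so two assessors could differ; the plateau gap remains; and the previous-day values are still needed.
- **Complications are probably ascertained from routine care.** Blood cultures and drain bilirubin, which the other definitions use, are not scheduled either, and the data form has an unspecified postoperative laboratory item. A reader might infer that liver failure cannot be assessed at all. The documents do not support that, because routine tests could supply the values. They support only that the scheduled tests do not, and that nothing makes testing equal across groups.
- **The size is assumed.** A reader might take 25% or 63% as the expected false-positive rate. Those are exact results for flat, independent values tested daily, and the documents give no variability. With fast recovery almost nobody is flagged.

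The impact is also bounded. Liver failure is one component of an outcome listed under safety. Liver function recovery is measured mainly by the biochemical panel.

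**Conclusion.** The point holds for limb 1 as written. It has no reference level, so it can count trivial joint rises. It misses a high flat course when limb 2 does not apply. The scheduled tests provide no day pair on which to judge it.

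The gap between definition and schedule follows from the text alone. The share wrongly flagged does not: about 0.1% to 44% by POD6 is a range over assumed courses with independent fluctuations, higher if the tests move together, and it depends on how many days are tested. That arms would differ in testing frequency is a risk created by open, self-selected grouping, not something that the documents show.

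The primary endpoint, albumin, and its sample size are unaffected. The definition should be corrected because the plan compares complication rates between groups and names them in its primary purpose.

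**What to change.** This changes an outcome definition and data collection only.

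1. In Section 7.2, 1c, keep limb 2.
2. Define *elevated* (bilirubin and INR) and *hyperbilirubinemia* against a fixed reference that the study has: the laboratory's upper limit of normal and, where the admission value is already abnormal, the patient's own admission value. Bilirubin is already drawn on admission, and coagulation is already on the pre-surgical form.
3. In Sections 3.2 and 6.3, add INR to the existing POD6 draw, so that every patient is classified at least once on the same day.
4. Report events found only from unscheduled tests separately, by group. A single fixed day can miss later onset, and this keeps such events visible without mixing two kinds of ascertainment.

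**Cost.** Some wording, and one added assay on blood already drawn.

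**Downside.** A fixed-reference rule ignores direction and may count patients who are still recovering on POD6. For illustration, assume that bilirubin falls 10% and INR 3% a day from POD1 to POD6. The shares remaining are 0.9^5 = 0.59 and 0.97^5 = 0.86. Noise aside, a patient whose POD1 values exceed 1/0.59 = 1.69 times the bilirubin reference and 1/0.86 = 1.16 times the INR reference would still be above both on POD6. The error rate of the revised rule has not been estimated, so the sponsor should acknowledge this limit when reporting the rate.
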